7.2 Statistical Methods

Descriptive Statistics

Descriptive statistics will be used to describe the average time of the total procedure, patients' tolerance and satisfaction level about the procedure. Paired t-test will be used to compare the suspicious lymph nodes and suspicious osseous lesions in the pelvis and extrapelvic regions detected by hybrid C11-choline PET/MR and pelvic multiparametric MRI method and by conventional CT and bone scan to investigate if the new method is able to detect more lymph nodes and osseous lesions compared to the conventional method. Paired t-test will also be used to compare the average SUV of lymph nodes and osseous lesions in the pelvis and extrapelvic regions by new method with that by conventional method to investigate if the new method provided more clarity in terms detecting the lymph nodes and lesions compared to the old method. If the patients' biopsy and surgery results available, sensitivity, specificity, positive predictive value and negative predictive value of detecting malignant lymph nodes and osseous lesions by the new method and by conventional method will be estimated and compared using McNemar's test.

Handling of Missing Data

As the sample size is 20 and imaging is completed over one day, no missing imaging data is anticipated.

Multiplicity

In current project, there is one primary objective and we don't have to adjust for multiple comparison.

Interim Analysis

There will not be interim analysis for the study.

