1.5 Risks and Benefits

C-11 choline is involved in phosphorylation process integrated into phospholipids in the cell membrane as part of phosphatidylcholine, which is vital in prostate cancer cell. The main risk involves the exposure to the radioactivity associated with the C-11 isotope incorporation. This exposure has been calculated to be much lower than the F-18 FDG. In addition, there is no radiation risk related to MR scan. For MR safety concern, each subject will undergo MR safety screening performed by PET/MR technologist prior to imaging.

2 Study Objectives

Primary Objective:

- 1) Test whether a hybrid combination of focused C-11 choline PET/MR and pelvic mpMRI on a PET/MR system is feasible

Secondary Objective(s):

- 1) Determine the efficacy (added values) of a hybrid combination of molecular focused C-11 choline PET/MR and functional and anatomic pelvic mpMRI in comparison with clinical findings.
- 2) Determine the efficacy (added values) of a torso C-11 choline PET/MR in comparison with conventional CT and bone scan in depicting metastasis to lymph node and bone.

3 Study Design

This study will be a prospective study to test and optimize the feasibility of hybrid 3T PET/MR scan in diagnosing and staging high and very high risk prostate cancer patients.

The FDA approved C-11 choline PET tracer at a dose of 12-14 mCi will be administered intravenously prior to fused PET/MR scan, and prior to diagnostic pelvic mpMRI scan while patient lying in the scanner.

In addition, single dose of Gadavist® (Gadobutrol, Bayer) is at no more than 0.1 mmol/kg will be administered intravenously for pelvic mpMRI.

The whole imaging procedure will be conducted on an FDA approved GE SIGNA 3T PET/MR scanner.

The C11-choline PET/MR and pelvic mpMRI findings and results will be compared with serum PSA level, Gleason score, clinical CT and nuclear medicine whole body bone scintigraphy findings, and histopathological results obtained through standard of care management.

Our primary interest is to investigate the feasibility of hybrid C11-Choline PET/MR fusion and pelvic mpMRI in imaging primary prostate cancer.

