3.4 Primary Study Endpoints

Patient: Completion of all imaging examinations with laboratory results.

Data analysis:

Objective 1: Descriptive study. With biopsy and/or surgical histopathology as gold standard, the sensitivity, specificity and accuracy of PET/MR will be calculated.

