3.7 Identification of Source Data

The following source data will be directly recorded on the Case Report Form (CRF):

- Vital signs
- Events
- Dosage of C-11 choline, route of administration
- Patient Reported Outcomes

The following source data will not be directly collected in the Case Report Form (CRF), but will be captured in supportive documentation (study source documents, EMR):

- Laboratory results can be utilized from outside facilities for this study
- Prostate biopsy reports and pathology reports can be utilized from outside facilities for this study.

4 Subject Selection Enrollment and Withdrawal

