6.3 Day 2- Follow up Procedures

1. Research coordinator will call patient to ask if patient has experienced fever, shortness of breath, palpitations, headache or other symptoms. If any of the above have been experienced, investigator MD is immediately notified.
2. Investigator MD is notified of results by the research coordinator. MD will sign and date source document.
3. All pre-data analysis study data forms and consent are confirmed intact and in the study binder. Binder is kept in a secured file cabinet in the research coordinators office.

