6.4 Schedule of Events

Study Activity	Day 0	Day 1	Day 2 (follow up)
Informed consent	X		
Medical records review. Confirm study inclusion criteria. Data recorded on source document.	X		
Subject eGFR determined. Labs obtained if Current serum creatinine is unavailable.	X		
Vital signs prior to and following imaging sessions recorded on source document (sitting blood pressure, respiratory rate, temperature, heart rate)		X	
Torso PET/MR fusion scan		X	
Pelvic mpMRI (SOC)		X	
Adverse event evaluation. Results recorded on source document.		X	
Follow-up call to collect adverse events. Result recorded on source document.			X

7 Statistical Plan

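### Procedure time, tolerance and satisfaction are to be reported, but the protocol does not say when or how they are collected, and the completers-only population would leave out men who could not tolerate the session

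*Combined protocol and SAP*

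**What the plan says.** Section 7.2 plans to describe the mean duration of the whole procedure and patients' "tolerance and satisfaction level about the procedure". It gives no scale, time point or definition for any of the three measures.

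Section 2 makes feasibility the primary objective: "Test whether a hybrid combination of focused C-11 choline PET/MR and pelvic mpMRI on a PET/MR system is feasible". The patient-level primary endpoint in 3.4 is "Completion of all imaging examinations with laboratory results".

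Section 3.7 includes "Patient Reported Outcomes" among the items entered directly on the CRF, without naming an instrument. Procedure times are not among the items listed there.

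Section 6.3 has the coordinator telephone on Day 2 to "ask if patient has experienced fever, shortness of breath, palpitations, headache or other symptoms". The matching row in 6.4 reads "Follow-up call to collect adverse events".

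Section 7.3 limits the analysis to men who finished every study procedure and the follow-up. Section 4.4 withdraws a man who cannot finish the PET/MR because of claustrophobia, and replaces men who withdraw early. Section 4.4.1 also allows withdrawal for discomfort. Section 4.4.2 keeps the data gathered up to withdrawal and has the Day 2 contact made regardless.

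**The concern.** The statistical section promises three summaries that the procedures section does not set up. A tolerance or satisfaction rating has to be asked for at or near the session; if it is not, an analyst cannot reconstruct it. If it is asked at different times or in different words from man to man, 20 answers will not make a coherent summary.

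The analysis population adds a second problem. Whether men can get through a session of more than an hour is a natural question for a feasibility pilot, and the men most informative about it are those who stop. The plan removes them from the analysis and recruits others in their place. Even well-collected tolerance data would then describe only men who had already shown that they could finish.

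**Working it through.** The first part is a comparison of sections. The second needs one line of arithmetic.

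**Where each measure could come from**

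- *Day 0 (6.1):* consent, records review, eGFR and preparation instructions. None of the three measures.
- *Day 1 (6.2):* vital signs, discussion with the patient, injection, two scans, vital signs, discharge. The minutes beside the scans are expected durations; there is no instruction to record actual times and no rating is taken.
- *Day 2 (6.3):* symptoms only.
- *Schedule (6.4):* consent, records review, eGFR, vital signs, the two scans, adverse-event evaluation on Day 1 and the adverse-event call on Day 2. No row for times, tolerance or satisfaction.
- *CRF list (3.7):* a patient-reported item that could hold tolerance and satisfaction, with no instrument, scale or time point. No procedure times.
- *Indirect sources:* adverse-event questioning at each contact (8.2) and withdrawals for claustrophobia or discomfort (4.4, 4.4.1) bear on tolerance. Automated instrument records, named in 9.2 as one example of source data, might give scan times; the protocol does not say they will be used.

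Satisfaction therefore rests entirely on the undefined CRF item. Total procedure time rests on records that no section designates. Tolerance has indirect sources only.

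**Is actual duration already known?** The protocol's own figures differ:

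- Section 6.2: 20-30 plus 40-45 gives 60-75 minutes.
- Figure 1 table: 25-30 plus 45-50 gives 70-80 minutes.
- Section 3.3: 70-80 minutes in the patient flow and 75-80 minutes in the technique description.
- Study Summary: 90 minutes of participation.

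The time actually taken is thus something the pilot has to measure.

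**Effect of the analysis population.** Let w be the number of injected men who cannot finish and are replaced until 20 complete (3.2). The documents give no value for w, so the values below are assumptions.

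- Completion in the 7.3 population: 20/20 = 100%, whatever w is.
- Completion among all injected men: 20/(20 + w).
- w = 1: 20/21 = 95.2%.
- w = 2: 20/22 = 90.9%.
- w = 4: 20/24 = 83.3%.

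A tolerance summary behaves in the same way: the w men who stopped because they could not tolerate the session contribute nothing. The error always runs towards good tolerance. Section 4.4 states the replacement target as 10 rather than 20, which needs reconciling, but the argument is the same with either number.

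**The case against.** A reader might infer from section 6 that these data would not exist and that no man would have a rating. The documents do not support that. Section 3.7 lists a patient-reported item as recorded on the CRF, and 9.3 requires everything the CRF asks for to be recorded and gaps to be explained. The CRF itself is not in the documents, so what it asks, and when, is unknown.

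Tolerance is also not wholly uncollected. The schedule has an adverse-event evaluation on Day 1, 8.2 requires specific questioning at each contact, the Day 2 call is open to other symptoms, and stopping for claustrophobia or discomfort is an event the protocol recognises. Section 7.2 does not say that tolerance must be a rating. Scan times may be recoverable from the scanner.

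A reader might also infer that the patient-side evidence for the primary objective would be lacking. That goes too far as well: completion is patient-side evidence, it is the named endpoint, and it is collected. Section 7.2 does not itself tie time, tolerance and satisfaction to feasibility; the link is a reasonable inference because they are the items in section 7 that describe the procedure rather than detection.

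On the population, 4.2 already excludes men known not to tolerate MRI, so few may stop early, and some withdrawals under 4.4 follow refusal of clinical imaging rather than intolerance.

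All of this limits the point without removing it. An undefined CRF item does not fix what is asked or when, adverse events say nothing about satisfaction, and acquisition times need not equal total procedure time, which 7.2 leaves undefined. Few early stops would make the bias small, but 7.3 would still hide them.

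**Conclusion.** The point holds as a gap between sections. Sections 7.2 and 3.7 imply time and patient-reported data; section 6 and the schedule do not say when or how they are obtained. Satisfaction and total procedure time may be absent or inconsistent, with satisfaction the most exposed. Tolerance is captured only indirectly.

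Separately, 7.3 combined with replacement under 4.4 biases any tolerance summary towards good tolerance and makes completion 100% by construction in the analysed set. The direction is certain if any injected man stops because he cannot tolerate the session; the size depends on how many do, which the documents do not allow to be estimated.

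The conclusion assumes that the CRF adds no timing or instrument beyond what the protocol describes. If it does, the first part reduces to citing it in sections 6 and 6.4; the second part is unaffected. The change should be made, because ratings not taken on the day cannot be recovered, but the trial can run and report its named endpoint without it.

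**What to change.** 1. In 6.2, add a step before discharge, or at the moment of stopping for a man who ends early, with one short tolerance item and one satisfaction item in fixed wording. State in 3.7 that these are the patient-reported items meant there.
2. In the same step, record clock times for entering the suite, injection, end of Part 1, end of Part 2 and leaving the table. Add procedure times to the CRF list in 3.7, and define in 7.2 which interval is the total procedure time.
3. Add a Day 1 row to 6.4 for the ratings and times.
4. Amend 7.3 so that time, tolerance, satisfaction and completion are summarised in every injected man, including those withdrawn, whose data 4.4.2 already retains. Without this amendment, steps 1 to 3 would collect data from men who stop early and then exclude them. The population for the imaging comparisons need not change for this purpose.

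The cost is roughly one CRF page and a few minutes per man (an estimate), plus a protocol wording change. No visit or scan is added. The tolerance figures may look slightly less favourable than under the present 7.3.

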1.3 Clinical Data to Date

Since 2000, there have been several studies investigating clinical role of choline PET and PETCT in diagnosing and staging primary prostate cancer. However, there is limited sensitivity and specificity in differentiating primary prostate cancer from normal prostate tissue due to overlapping choline uptake by hyperplastic prostate tissue, high-grade intraprostatic epithelial neoplasia (HGPN), prostatitis, BPH, even urinary excreted activity in the base of urinary bladder and urethra. In addition, there is no proven significant correlation between C11-choline uptake by localized primary prostate cancer and serum PSA level, Gleason score^{7,8}. Therefore, there is clinical consensus of limited clinical value of choline PET and PETCT in characterizing primary PCa.

However, the pursuit of combined advantages of choline PET and pelvic mpMRI in PCa persists. In one recent clinical trial, it is found that fused F18-Choline PET/MR images could provide added value for MR guided transrectal prostate biopsies⁹.

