* Axial T1-weighted LAVA-FLEX acquired in Part1. may be used for pre-contrast T1-weighted images.

Image review:

- PET/MR fusion study, including PET emission data, MRAC image and focused pelvis PET/MR fusion images will be sent to MIM Vista workstation for review by an independent, experienced board certified nuclear medicine radiologist without knowing clinical findings except for high risk prostate cancer.
- Focused mpMRI of pelvis images will be sent to PACS for review by an independent, experienced board certified body MR radiologist without knowing clinical findings except for high risk prostate cancer.

Evaluation of imaging findings:

Reviewers review images to evaluation imaging findings without knowing clinical findings except all subjects are recently diagnosed with very high-risk or high-risk prostate cancer. Readout workflow is illustrated in Figure 2. The scores will be recorded and stored in a secured REDCap file.

Pelvic mpMRI:

1. Lesion detection and characterization utilizing PI-RADS version 2 (15).
2. Tumor staging utilizing AJCC TNM staging system (3)
3. Detection of suspicious pelvic lymph nodes.
4. Detection of suspicious osseous lesion in the pelvis.

Torso and focused C-11 choline PET/MR:

1. Lesion detection and characterization.
2. Tumor staging
3. Detection of suspicious pelvic and extrapelvic lymph nodes.
4. Detection of suspicious osseous lesion in the pelvis and extrapelvic regions.
5. Document SUV in the region of interest (ROI) if possible.

Reference standards

[figure not shown]
[figure not shown]

1. Histopathology results when available
2. Clinical imaging study (CT, bone scan, etc).
3. Clinical follow-up (progression or regression at follow-up routine clinical imaging after treatment).

Prostate tumor localization and characterization: Focused C-11 choline PET/MR and pelvic mpMRI findings to be correlated with clinical prostate biopsy and surgery results.

Lymph node metastases: Torso and focused C-11 choline PET/MR and pelvic mpMRI findings to be correlated with clinical CT, lymph node biopsy, and surgery results

Bone metastases: Torso and focused C-11 choline PET/MR and pelvic mpMRI findings to be correlated with whole body bone scan, F-18 NaF PET/CT (if available), CT, dedicated MRI, and biopsy results.

Figure 1. Illustration of Part 1 “Torso C-11 Choline PET/MR” and Part 2 “Hybrid Focused C-11 Choline PET/MR and Pelvic mpMRI.”

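### The lesion-count test in Section 7.2 does not separate true from false calls, so a significant excess of suspicious nodes and bone lesions could come from false positives alone

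*Combined protocol and SAP*

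**What the plan says.** Section 2 (Study Objectives) sets secondary objective 2: "Determine the efficacy (added values) of a torso C-11 choline PET/MR in comparison with conventional CT and bone scan", with metastasis to lymph node and bone as the target.

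Section 7.2 (Statistical Methods) then gives two analyses for nodes and bone.

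- A lesion count: "Paired t-test will be used to compare the suspicious lymph nodes and suspicious osseous lesions in the pelvis and extrapelvic regions". The two sides are PET/MR with pelvic mpMRI against CT with bone scan. The stated purpose is "to investigate if the new method is able to detect more lymph nodes and osseous lesions compared to the conventional method".
- An accuracy analysis: "If the patients' biopsy and surgery results available, sensitivity, specificity, positive predictive value and negative predictive value" are to be estimated for each method and compared with McNemar's test.

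The count is built from reader output. The image evaluation list in Section 3.3 asks the PET/MR reader for "Detection of suspicious pelvic and extrapelvic lymph nodes", and likewise for suspicious bone lesions. The reference standards in the same section begin with "Histopathology results when available", followed by clinical imaging such as CT and bone scan, and then clinical follow-up. Section 7.2 does not link the lesion count to any of these.

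Elsewhere the plan is framed around accuracy. Section 3.4 takes histopathology as the gold standard for sensitivity, specificity and accuracy of PET/MR. Section 7.1 bases the sample size on accuracy in identifying patients with malignant nodes.

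**The concern.** A suspicious lesion is a reader's call; a metastasis is a fact about the patient. Section 7.2 counts the first, while the objective concerns the second. In its statement of purpose the section drops the word suspicious, so reader calls go into the test and detected lesions come out of it.

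The test rises with every extra call on the new method, true or false. Sensitivity, specificity and predictive values would tell these apart, but they depend on tissue that the plan does not guarantee. The count needs no tissue, so it can always be run, and it does not change when tissue is available.

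At stake is the meaning of one secondary result. A statement that the new method finds significantly more nodal and bone lesions could be read as better depiction of metastasis when the data cannot show that.

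**Working it through.** **1. The plan's own figure.** The only power stated is 82%, in Section 7.1, for a two-sided 0.05 McNemar test with n = 20, accuracy difference d = 0.30 and discordant proportion ψ = 0.31. The Miettinen approximation is

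power = Φ[(d√(nψ) − 1.96ψ) / √(ψ² − d²(3+ψ)/4)]

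= Φ[(0.747 − 0.608) / √(0.0961 − 0.0745)] = Φ(0.139/0.147) = Φ(0.948) = 82.8%.

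This agrees with the stated figure to within a point. It belongs to the accuracy test. No power or expected difference is given for the t-test on counts.

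**2. Inputs for the count test.** n = 20 is from Section 7.1. Section 7.2 states no level or sidedness for the t-test, so I assume two-sided 0.05, as in Section 7.1. The documents give no false-positive rate for nodes or bone lesions and no SD for counts, so every rate and SD below is an assumption.

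**3. How small an excess is enough.** The critical mean difference, in SDs of the paired differences, is t(0.975, 19)/√20 = 2.093/4.472 = 0.468.

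**4. Identical true findings, a few extra false calls.** Let k of 20 patients have one extra false call on the new method and let all other differences be 0. The mean difference is k/20 and the sample variance is k(20 − k)/(20 × 19), so t = √[19k/(20 − k)].

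| k | t | p |
|---|---|---|
| 3 | √(57/17) = 1.83 | 0.083 |
| 4 | √(76/16) = 2.18 | 0.042 |
| 5 | √(95/15) = 2.52 | 0.021 |

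If only confirmed lesions are counted, every difference is 0 and there is no gain.

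**5. Sensitivity to the spread of counts.** With a mean excess of one false call per patient, t = 1/(SD/√20):

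- SD 1.5: t = 2.98, p = 0.008
- SD 2.0: t = 2.24, p = 0.038
- SD 2.5: t = 1.79, p = 0.090

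**6. Sensitivity to the false-call rate.** This is a simulation of 40,000 trials of 20 patients with equal true findings and Poisson false calls. It gives the chance that the t-test is significant in favour of the new method:

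| False calls per patient, new method | Conventional 0 | Conventional 0.1 |
|---|---|---|
| 0.1 | 10% | 1.6% |
| 0.2 | 43% | 10% |
| 0.3 | 72% | 25% |
| 0.5 | 96% | 62% |

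The result turns on the imbalance in false calls between the methods. When both have 0.1 per patient, a false signal is rare.

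**The case against.** The strongest reply is that the plan does not rest on this test. It stands under the Descriptive Statistics heading, no success rule is attached to it, and the text never says that more is better. The powered hypothesis and Section 3.4 concern accuracy, and Table 1 names pathology as the reference in every node and metastasis row. The primary objective is feasibility, Section 3.5 lists no secondary endpoints, and Section 4.2 says the research scan does not replace clinical imaging. All of this stands, and it limits the point to the lesion-count test.

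Four stronger readings are tempting but not supported.

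- That the plan would declare the new method superior on counts. No such rule is written.
- That counts would be the main evidence in most subjects. Pathology is conditional, but its expected availability is not given.
- That the new method is bound to score higher because it pools two reads. The comparator also has two tests. Table 1 lists pelvic mpMRI under clinical imaging, and the readout workflow is in a figure not available here.
- That the plan's own background shows false positives at these sites. Section 1.3 says "there is limited sensitivity and specificity in differentiating primary prostate cancer from normal prostate tissue", which concerns uptake within the prostate, not nodes or bone.

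Nor does a less specific method always win. A more sensitive one also gains, and the count cannot say which has happened. The accuracy analysis does not remove this difficulty, because it may not be possible to run it and it leaves the t-test as it is.

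**Conclusion.** The concern holds for the lesion-count t-test in Section 7.2 and no further. As written, the test cannot distinguish more metastases from more false calls, although it serves an objective about metastasis. With identical true findings, one extra false call in 4 of 20 patients would give p = 0.042, assuming a two-sided 0.05 test, 20 evaluable patients and no extra false calls on the conventional side.

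The figures show how the test behaves. They do not predict this trial's false-positive rate, which the documents do not allow anyone to estimate. The accuracy analyses are not affected. The change is worth making because it is cheap and brings the comparison into line with the objective.

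**What to change.** In Section 7.2:

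- Classify each suspicious node and bone lesion, for each method, as confirmed, refuted or unverified. Use pathology or the routine clinical follow-up already listed in Section 3.3. Do not use the CT or bone scan being compared, although Section 3.3 also lists them as references. State in advance what follow-up finding counts as confirmed or refuted.
- Report all three counts for each method, including refuted (false-positive) lesions per patient.
- Base any statement on added value on confirmed lesions read together with refuted ones.
- Keep the raw suspicious-lesion count as descriptive only, with no inference that more is better.

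The cost is SAP wording, one status field per lesion, and the work of reading that status from clinical records. The scheduled study contacts end with the Day 2 call, the summary gives an overall duration of 16 weeks, and Section 3.3 sets no timing for follow-up, so a cut-off date for verification is needed. No extra biopsy or imaging is asked for.

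The downsides should be stated in the plan. Many lesions may stay unverified, and fewer will support the comparison. Lesions seen only on PET/MR may also be verified more often than others, which is verification bias. The unverified count for each method must therefore stand beside the result.

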Acquisition time per table bed	Part 1: Torso C-11 choline PET/MR				Part 2: Hybrid dedicated focused C-11 choline PET/MR and pelvic mpMRI			
2-5 min/bed	PET		AC	Diagnostic MR pulse sequences				
2-5 min/bed	PET		AC	Diagnostic MR pulse sequences				
2-5 min/bed	PET		AC	Diagnostic MR pulse sequences				
2-5 min/bed	PET		AC	Diagnostic MR pulse sequences				
2-5 min/bed	PET		AC	Diagnostic MR pulse sequences				
2-5 min/bed	PET				Focused C-11 choline PET/MR 		Pelvic mpMRI (anatomic and functional sequences) without e-coil	
Time	25-30 min				45-50 min			

AC=attenuation correction

mpMRI = multiparametric MRI

e-coil = endorectal coil (for illustration purpose only, will not be used in current study)

* = F-18 FDG PET/MR shown for illustration purpose

** = C-11 choline PET/CT shown for illustration purpose

*** = T2W shown for illustration purpose

Figure 2. Workflow of Readout Sessions (parts 1-3)

[figure not shown]

Table 1. Summary of imaging finding evaluation

	C-11 choline PET/MR (research)	Clinical imaging exams	Reference standard	Findings
Local T staging: Prostate	Focused pelvic C-11 choline PET/MR	Pelvic mpMRI	Pathology results (biopsy, surgery if available)	Localization Characterization Local tumor (T) staging
Metastasis to pelvic lymph nodes(N)				
Pelvis	Focused C-11 choline PET/MR	Pelvic mpMRI CT	Pathology results (biopsy, surgery if available)	Localization SUV values
Torso	Torso C-11 choline PET/MR	CT	Pathology results (biopsy, surgery if available)	Localization SUV values
Metastasis to pelvic bone (M)				
Pelvis	Torso and focused C-11 choline PET/MR	Pelvic mpMRI CT Bone scan	Pathology results (biopsy, surgery if available)	Localization SUV values
Extra-pelvis	Torso C-11 choline PET/MR	CT Bone scan	Pathology results (biopsy, surgery if available)	Localization SUV values
Visceral metastasis (M)				
Visceral metastasis (M)	Torso C-11 choline PET/MR	CT	Pathology results (biopsy, surgery if available)	Localization SUV values

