7.1 Sample Size Determination

Our null hypothesis is the hybrid C11-choline PET/MR and pelvic multiparametric MRI will have an equal accuracy of detecting patients with malignant lymph nodes in the very high risk/high risk prostate cancer patients compared to that in the conventional CT and bone scan method. With 20 patients, a McNemar's test with a 0.05 two-sided significance level will have 82% power to reject the null hypothesis if the difference in accuracy of the two methods is 0.3 or greater and assume discordant pairs is expected to be 0.31.

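### Section 7.2 tests SUV against CT and bone scan, for which no SUV is defined, and uses McNemar's test for PPV and NPV, which it does not compare

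*Combined protocol and SAP*

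**What the plan says.** Section 7.2 lists three comparisons between the hybrid PET/MR plus mpMRI method and the conventional method, which it names as CT and bone scan.

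- **Lesion counts.** A paired t-test on suspicious nodes and bone lesions, "to investigate if the new method is able to detect more lymph nodes and osseous lesions compared to the conventional method".
- **SUV.** A paired t-test to "compare the average SUV of lymph nodes and osseous lesions in the pelvis and extrapelvic regions by new method with that by conventional method", with the stated aim "to investigate if the new method provided more clarity in terms detecting the lymph nodes and lesions compared to the old method".
- **Diagnostic accuracy.** Where biopsy and surgery results exist, sensitivity, specificity, PPV and NPV "will be estimated and compared using McNemar's test". No other method is named for any of the four.

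Four other places bear on these.

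- Section 3 identifies the bone scan as whole body scintigraphy.
- Section 3.3, in the reading list for C-11 choline PET/MR, says "Document SUV in the region of interest (ROI) if possible". The mpMRI list has no SUV item, and CT and bone scan have no reading list.
- Section 3.3 gives the first reference standard as "Histopathology results when available", and Table 1 likewise makes surgical pathology conditional on availability.
- Section 7.1 frames its hypothesis per patient, as "equal accuracy of detecting patients with malignant lymph nodes". Section 7.2 does not state the unit for its four accuracy measures.

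**The concern.** Secondary objective 2 (section 2) is the comparison of torso PET/MR with CT and bone scan for nodal and bone metastasis. Two of the planned comparisons that serve it fail as written.

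A paired t-test needs a value from each method for every pair. If SUV exists on one side only, the test returns nothing and the question about clarity goes unanswered.

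McNemar's test compares two proportions taken over the same patients. PPV is the fraction correct among a method's own positive calls, and NPV the fraction correct among its own negative calls, so the two methods are judged on different, partly overlapping sets of patients. A McNemar p-value printed beside PPV or NPV would describe another quantity. An analyst who saw the problem only at analysis would have to choose a substitute after seeing the data.

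**Working it through.** **Plan's own figure.** The only related number is the 82% power in section 7.1, for a McNemar comparison of patient-level accuracy (n = 20, difference d = 0.30, discordant proportion ψ = 0.31, two-sided 0.05). Miettinen's approximation gives

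Φ[(d√(nψ) − 1.96ψ) / √(ψ² − d²(3+ψ)/4)] = Φ[(0.747 − 0.608) / 0.147] = 0.828,

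close to the stated value. Exact McNemar power on the same inputs is 0.569. That is a separate matter, and nothing below depends on either figure.

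**Part (a): is there a second SUV?**

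| Source | SUV for the conventional method? |
|---|---|
| 7.2, comparator | CT and bone scan; no SUV defined |
| 3.3, PET/MR reading list | SUV requested, for PET/MR only |
| 3.3, mpMRI reading list | No SUV item |
| 3.3, Table 1 | SUV in a findings column set per row and not tied to a modality |
| 3.3, F-18 NaF PET/CT | Optional, bone reference only, different tracer, outside the defined comparator |

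In Table 1 the torso node row and the visceral row name CT as the only clinical examination and still list SUV, so the entry is best read as referring to PET/MR. As the documents stand, no pair can be formed.

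**Part (b): does McNemar's test address PPV and NPV?**

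PPV = TP/(TP+FP) and NPV = TN/(TN+FN), each computed within one method's own calls. The exact two-sided McNemar p-value uses only the two discordant counts b and c, and equals 2·P(X ≥ max(b,c)), capped at 1, with X ~ Binomial(b+c, ½).

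The following counts are assumed for illustration: 20 verified patients, 8 node-positive and 12 node-negative. Cells show new/conventional calls.

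| | ++ | +− | −+ | −− |
|---|---|---|---|---|
| A, node-positive | 4 | 3 | 0 | 1 |
| A, node-negative | 0 | 3 | 0 | 9 |
| B, node-positive | 4 | 4 | 0 | 0 |
| B, node-negative | 2 | 2 | 0 | 8 |

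Results, new versus conventional:

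| | Table A | Table B |
|---|---|---|
| Sensitivity | 7/8 vs 4/8 (3 vs 0, p = 0.25) | 8/8 vs 4/8 (4 vs 0, p = 0.125) |
| Specificity | 9/12 vs 12/12 (0 vs 3, p = 0.25) | 8/12 vs 10/12 (0 vs 2, p = 0.50) |
| Accuracy | 16/20 vs 16/20 (3 vs 3, p = 1.0) | 16/20 vs 14/20 (4 vs 2, p = 0.69) |
| Positive calls | 10 vs 4 (6 vs 0, p = 0.031) | 12 vs 6 (6 vs 0, p = 0.031) |
| PPV | 7/10 vs 4/4, −30 points | 8/12 vs 4/6, 0 points |

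Section 7.2 does not say which 2×2 table McNemar's test would use for PPV. No choice works:

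- *All positive calls.* p = 2 × (½)⁶ = 0.031 in both tables, whether the PPV difference is −30 points or none. This tests the positivity rate.
- *Correctness in all patients.* In Table A p = 1.0, although PPV is 70% vs 100% and NPV is 9/10 = 90% vs 12/16 = 75%. This tests accuracy.
- *Patients in both PPV denominators.* In Table A these are the 4 patients positive on both methods. They are right or wrong on both together, so b = c = 0 by construction and there is nothing to test.

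**Precision of any PPV comparison.** In Table A the exact 95% intervals are 35–93% for 7/10 and 40–100% for 4/4. A patient-level bootstrap of the PPV difference (20,000 resamples) gives −60 to 0 points in Table A, with 1.2% of resamples undefined, and −31 to +32 points in Table B.

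**The case against.** The strongest reply is that little hangs on this. The study is a 20-patient pilot whose primary objective is feasibility. Section 3.5 lists no secondary endpoints, and the Study Summary and section 3.4 promise only descriptive sensitivity, specificity and accuracy. PPV and NPV comparisons appear only in section 7.2, under a descriptive heading and conditional on biopsy and surgery results. An SUV test without data cannot mislead; it would simply be dropped. This limits the severity. It does not excuse the text, because section 7.2 prescribes inferential tests and section 2 makes the comparison a secondary objective.

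Second, no passage says outright that CT or bone scan lacks an SUV, and Table 1 and the optional F-18 NaF PET/CT leave some room. It is fair to say that the documents define no conventional SUV, and the conclusion is put that way. Neither source supplies a valid comparator.

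Third, the tables are invented and chosen for contrast. They show the principle and do not predict this trial's result.

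Fourth, the bootstrap behaves badly in Table A. The conventional method has no false positives there, so its PPV is 100% in every defined resample and the upper limit of zero is forced. That stands, and it favours reporting intervals without a formal comparison.

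Finally, McNemar's test is sound for half of the accuracy sentence, and the t-test on lesion counts can be run. Both are accepted.

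**Conclusion.** The concern holds on both parts; the text should be corrected before analysis.

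- **SUV.** The test has no second member of the pair under the documents as they stand. This rests on section 7.2's own definition of the conventional method and on SUV being requested only for PET/MR.
- **PPV and NPV.** McNemar's test does not address a difference in either. This follows from the differing denominators and does not depend on the illustrative counts, which show one p-value (0.031) alongside PPV differences of −30 and 0 points.

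The reach is limited to secondary objective 2. Feasibility, the patient-level accuracy comparison in section 7.1, McNemar's test for patient-level sensitivity and specificity, and the estimation of PPV and NPV all stand.

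Two lesser points go with this. A higher count of suspicious lesions is not by itself better detection, since the findings are unverified. The unit of analysis for the accuracy measures in section 7.2 also needs stating.

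**What to change.** 1. Delete the SUV comparison with the conventional method. Summarise PET/MR SUV descriptively, by reference status where lesions are verified.
2. Keep McNemar's test for patient-level sensitivity, specificity and accuracy.
3. Report PPV and NPV for each method with exact confidence intervals. If they are compared, name a paired predictive-value method in advance, such as the generalized score test or a patient-level bootstrap. State that performance is limited with at most 20 verified patients, and that the bootstrap degenerates when a method has no false positives.
4. Label the lesion-count result as unverified findings. Where reference results exist, also report confirmed and false-positive findings separately for each method.
5. State the unit of analysis, and allow for clustering within patient in any per-lesion accuracy figure.

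The cost is SAP wording and minor programming, with no new data and no change to study conduct. The verified summaries will cover only patients or lesions with reference results; unverified lesions stay unclassified.
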